4 ELIGIBILITY

- Subject population: Adolescents and young adults undergoing tonsillectomy
- Inclusion criteria
 - Adolescents and young adults aged 12-25 years will be eligible to be recruited if they undergo palatine tonsillectomy with or without adenoidectomy on the pediatric or general otolaryngology service of the University of Michigan Medical School, and if they are not:
 - Patients in foster care or patients with a legal guardian
 - Patients with developmental delays, such as autism
 - Patients who are non-English speaking
 - Patients with recent suicidal ideation
 - Patients undergoing emergent tonsillectomy

- Exclusion criteria for primary analysis analyzing prescribing
 - Patients who were approached for consent but declined
 - Patients with prescription opioid use prior to surgery
 - Patients undergoing additional major procedures at the same time as tonsillectomy
 - Patients enrolled in another study
 - Patients who are not prescribed opioids post-operatively
 - Patients who are enrolled in the “M-POP” pathway, which includes education about pain management and a small initial opioid prescription (10 doses)
 - Patients with hospitalization with length of stay > 1 day after surgery
- Additional exclusion criteria for secondary analysis examining patient-reported outcomes through surveys
 - Patients who were not reached for consent
 - Patients who do not complete the baseline and post-operative day 14 surveys
- Inclusion of vulnerable populations: The purpose of this study is to evaluate an intervention on opioid prescribing to adolescents and young adults. As such, minors must be included in the study.

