6 STUDY DESIGN AND PROCEDURES

- Study design
 - The study will use a difference-in-differences design in which changes before and after the intervention will be compared between a treatment group and a control group.
 - The treatment group will include all patients undergoing tonsillectomy at C.S. Mott Hospital by a pediatric otolaryngology faculty member at the University of Michigan.
 - The control group will include all patients undergoing tonsillectomy at University Hospital, Brighton Center for Specialty Care, or Livonia Center for Specialty Care by a general otolaryngology faculty member at the University of Michigan.
- Data collection procedures throughout the study
 - There will be three sets of surveys: a baseline survey, daily surveys on post-operative days 1-13, and a final survey on post-operative day 14. Post-operative surveys will be sent to all patients who enroll, including those who are not prescribed opioids post-operatively. These patients will not be included in the primary or secondary analysis but will be analyzed in a separate study examining pain recovery without opioids.
 - Baseline survey: Patients will be asked to complete a 10-15 minute survey assessing demographics, reason for tonsillectomy, current pain, chronic pain, history of opioid use, history of opioid misuse, family chronic opioid use, depression, substance use disorders, anxiety, sleep, and global health. Patients will be e-mailed a link to the baseline survey upon enrollment; for patients who cannot receive e-mail links, the survey will be administered over the phone. For patients at Mott or University Hospital recruited in-person, the baseline survey will be administered by a study team member in-person through Qualtrics on a tablet. Patients sent the baseline survey who do not complete it before surgery will be contacted via e-mail or by phone to remind them or approached in-person to complete it through Qualtrics on a tablet. If patients are contacted by phone, they will be given the option to complete the survey over the phone.

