10 STATISTICAL CONSIDERATIONS

- Outcomes in primary analysis
 - Number of doses in the discharge opioid prescription
 - Proportion of patients in which the number of doses in the discharge opioid prescription equals the number of doses in the new default settings
 - Proportion of patients prescribed opioids at discharge
 - Proportion of patients prescribed opioids at discharge who had at least one opioid prescription refill from UM during the two weeks after surgery
 - Proportion of patients who saw a UM provider in an office due to pain during the two weeks after surgery

- Proportion of patients with at least one emergency department visit or hospitalization at UM for pain during the two weeks after surgery
- Additional outcomes in secondary analysis (based on data from the final post-operative day 14 survey)
 - Overall satisfaction with pain control during the two weeks after surgery (scale of 1-10)
 - Proportion of patients who reported that their pain was well-controlled
 - Proportion of patients whose overall pain control was rated as much worse or worse than expected
 - Proportion of patients whose pain has resolved by day 14 after surgery
 - Pain score over the past 7 days at its worst (scale of 0-10)
 - Pain score over the past 7 days on average (scale of 0-10)
 - Number of opioid doses taken during the two weeks after surgery
 - Proportion of patients with leftover doses of opioids
 - Proportion of patients with leftover doses who disposed of them
 - Proportion of patients who misused opioids belonging to others at least once during the two weeks after surgery
 - Proportion of patients who misused their own opioids at least once during the two weeks after surgery
 - PHQ-8 score (depression)
 - Score on PROMIS Pediatric Anxiety – Short Form 8a
 - Score on PROMIS Sleep Disturbance – Short Form 8a
 - Proportion of patients who saw their primary care provider (or a colleague) in the office due to poorly controlled pain at least once during the two weeks after surgery
 - Proportion of patients who visited an urgent care center due to poorly controlled pain at least once during the two weeks after surgery
 - Proportion of patients who visited a retail clinic due to poorly controlled pain at least once during the two weeks after surgery
 - Proportion of patients who went to an emergency department and/or were hospitalized due to poorly controlled pain at least once during the two weeks after surgery

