- Data from the daily surveys will be used to assess whether daily opioid consumption reports matches the consumption reported on the final post-operative day 14, and will also be analyzed in a separate study assessing the trajectory of pain and opioid use after tonsillectomy.
- We will fit linear or logistic regression models assessing outcomes as a function of an indicator of post-intervention status, an indicator of treatment group status, and its interaction, controlling for covariates such as demographics (e.g., age, sex) and baseline co-morbidities (e.g., depression, anxiety). We will graphically and statistically assess the comparability of pre-intervention monthly trends in outcomes between the treatment and control groups.

- We hypothesize that there will be no change in outcomes in the control group (i.e., that the post-intervention trend in outcomes in the control group will be an extension of the pre-intervention trend in outcomes). In contrast, we hypothesize that the number of doses and opioid consumption will drop in the treatment group after the intervention; that the proportion of patients with prescriptions concordant with the new defaults will increase after the intervention; and that there will be no change in balancing measures such as pain control or depression.
- Sensitivity analyses
 - Statistical modeling: we will explore whether results change when replacing the indicator of treatment group status with a vector of fixed effects for the prescribing clinician, and will explore the feasibility of using an interrupted time series approach instead of a difference-in-differences approach.
 - We will determine whether any otolaryngology residents wrote opioid prescriptions for both a pediatric otolaryngology and general otolaryngology patients in the post-intervention period, and exclude data from any such residents from the analysis
 - We will exclude opioid prescriptions written for patients of the chief of pediatric otolaryngology, who will be involved in setting the new defaults
- Subgroup analysis will occur by age group (ages 12-17 years vs 18 and older), gender, payer type (private/public), and baseline co-morbidities (e.g., depression and anxiety).
- We will separately analyze data from pediatric otolaryngology patients undergoing surgery outside of Mott and general otolaryngology patients undergoing surgery at Mott to assess for any spillover effects.

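### Patients given no post-operative opioid are excluded from both analyses, so dose, visit, pain and survey outcomes are conditioned on a decision made after the intervention, and Section 10 conflicts with that exclusion

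*Combined protocol and SAP*

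**What the plan says.** Section 4 (Eligibility) lists among the exclusions for the primary analysis "Patients who are not prescribed opioids post-operatively". The survey-based analysis inherits this, because its own list is introduced as "Additional exclusion criteria for secondary analysis examining patient-reported outcomes through surveys". Section 6 (Study Design and Procedures) confirms the scope: "These patients will not be included in the primary or secondary analysis". It assigns them instead to a separate study of recovery without opioids. The same section says that follow-up continues in these patients: "Post-operative surveys will be sent to all patients who enroll, including those who are not prescribed opioids post-operatively".

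Section 10 (Statistical Considerations) lists "Proportion of patients prescribed opioids at discharge" as a primary-analysis outcome, beside "Number of doses in the discharge opioid prescription". The refill outcome carries its own restriction to patients prescribed opioids at discharge. The office, emergency department and hospital visit outcomes are worded over patients generally. For the safety side, Section 10 hypothesizes that "there will be no change in balancing measures such as pain control or depression". None of its sensitivity, subgroup or spillover analyses brings the excluded patients back.

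**The concern.** Whether a patient receives an opioid is decided after surgery. From October 1, 2020 the treatment group's clinicians make that decision with the new orderset in place. Restricting the analysis to prescribed patients therefore selects on something that happens after the intervention, and that the plan itself lists as an outcome.

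The difference-in-differences contrast does not remove the problem if the no-opioid share moves differently in the two groups, because the before and after samples are then selected differently. Adjusting for age, sex and baseline co-morbidities need not repair it. The outcome that would reveal such a shift is the proportion prescribed at discharge. Under the exclusion it is 100% in every group and period, if *post-operatively* in Sections 4 and 6 means the same as *at discharge* in Section 10. The documents do not say that it does.

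Two readings are at stake: the size of the fall in doses, and the balancing measures. A patient who receives no opioid and then has poor pain control or returns for pain cannot appear in any planned between-group comparison.

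**Working it through.** **The plan's own figures.** Section 10 gives 113 treatment and 85 control patients, and 65% consent for the surveys. 113 × 0.65 = 73.45 (stated 74), 85 × 0.65 = 55.25 (stated 55), and 198 × 0.65 = 128.7 (stated 129). These agree within rounding. The plan does not say whether 113 and 85 were counted before or after the no-opioid exclusion. It gives no no-opioid share, visit rate or pain-control rate, so everything below is illustration on assumed inputs.

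**Doses.** Assume the treated-group mean among prescribed patients falls from 30 (the current default) to 22, and the control group does not change in mean or in no-opioid share. Let p0 = 5% be the treated group's no-opioid share before the intervention and p1 the share after. Patients with no prescription count as 0 doses.

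- Prescribed-only effect: 22 − 30 = −8.0
- All-patient effect: (1 − p1) × 22 − (1 − p0) × 30 = (1 − p1) × 22 − 28.5

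**Poor pain control.** Assume 15% with an opioid and 40% without, in both periods. The prescribed-only change is 0. The all-patient change is (0.40 − 0.15) × (p1 − p0).

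| p1 | Prescribed-only doses | All-patient doses | Prescribed-only pain change | All-patient pain change |
|---|---|---|---|---|
| 5% (no change) | −8.0 | −7.6 | 0 | 0 |
| 10% | −8.0 | −8.7 | 0 | +1.25 points |
| 15% | −8.0 | −9.8 | 0 | +2.5 points |
| 20% | −8.0 | −10.9 | 0 | +3.75 points |

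The two dose effects differ by p0 × 30 − p1 × 22 = 1.5 − 22 × p1. This is zero at p1 = 1.5/22 = 6.8%. Below that share, the prescribed-only figure is the larger fall. In the no-change row, the gap between −7.6 and −8.0 reflects the different population averaged over, and the selection bias in pain is zero.

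**Direction.** Assume a 10% pain-visit rate among prescribed patients in both periods. The all-patient change is (rate without opioid − 0.10) × (p1 − 0.05). For p1 = 10%, 15% and 25%:

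- Rate of 20% without an opioid: +0.5, +1.0 and +2.0 points
- Rate of 30%: +1.0, +2.0 and +4.0 points
- Rate of 5%: −0.25, −0.5 and −1.0 points

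The sign depends on who goes without an opioid.

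**Selective movement.** Suppose 20% of patients would get 10 doses and 80% would get 20, a mean of 0.2 × 10 + 0.8 × 20 = 18. If the whole low-dose group moves to none, the prescribed-only mean rises to 20, while the all-patient mean falls to 0.8 × 20 = 16. The restricted and unrestricted analyses then point in opposite directions.

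**Scale.** If the 74 treated survey patients split evenly over the two 10-month periods (37 each), the non-zero pain shifts in the table are 0.0125 × 37 ≈ 0.5 to 0.0375 × 37 ≈ 1.4 patients.

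**The case against.** The strongest case is that the intervention changes the number that fills the doses field once an opioid is being ordered. Its route to the decision to prescribe at all is indirect. Section 10 predicts fewer doses, lower consumption and more concordance with the default, and predicts nothing about the share prescribed. Listing that share as an outcome shows that it is monitored, not that a change is expected. The current default is 30 doses, and the one named small-prescription pathway, M-POP, is excluded anyway, so a move from a small prescription to none is not obviously common. Section 2 concerns default settings for opioid prescriptions, so an effect among prescribed patients is a coherent target, and the exclusion is disclosed and consistent between Sections 4 and 6. Nor is harm wholly out of sight: enrolled no-opioid patients are surveyed, and Section 11.3 provides that reported poor pain control is passed to the surgical team.

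Most of this stands as a reason to expect a modest effect. It does not justify conditioning the pain, visit and mood outcomes on the prescription, and it does not resolve the conflict with Section 10. Individual follow-up is no substitute for a between-group comparison.

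A reader might infer that the excluded patients are those most exposed to under-treatment, that the no-opioid share would move only in the treatment group, or that the dose reduction is necessarily understated. The documents support none of these. No-opioid patients may have lower need. No share is given for either group or period. On the illustration above, understatement begins only above a post-intervention share of about 6.8%.

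**Conclusion.** The concern holds as a conflict between Sections 4 and 6 and Section 10, and as an unexamined source of selection bias. The conflict rests on the text alone; the one proviso is the meaning of *post-operatively*. The bias is conditional: the no-opioid share must change differently between groups. If it stays constant, the bias in pain and visits is zero. If both groups shift equally and have the same outcome rates, it cancels for those outcomes. The direction is not fixed by the documents.

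On the assumed inputs, the all-patient dose effect runs from -7.6 to -10.9 against a prescribed-only -8.0, and the unseen change in poor pain control runs from 0 to 3.75 points. These figures show the mechanism and are not estimates for this study. The plan should be changed because no analysis it contains would show whether the bias is present, and the correction is cheap.

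**What to change.** Reconcile Sections 4 and 6 with Section 10 as follows.

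- Keep otherwise eligible patients with no opioid prescription in the analysis population. Code discharge doses as 0 and take doses consumed as reported.
- Analyse doses, consumption, UM visits, pain outcomes, PHQ-8, anxiety, sleep and survey-reported utilization in all such patients (for survey outcomes, all who meet the survey-completion criteria).
- Restrict refills, leftover doses, disposal and misuse of the patient's own opioids to patients who were prescribed opioids. These outcomes presuppose having an opioid, and structural zeros would lower the leftover and misuse rates as prescribing falls.
- Keep the prescribed-only analysis of the other outcomes as a supplement.
- Report the no-opioid share by group and period.
- Use one term for *post-operatively* and *at discharge*, or define the difference.
- State whether 113 and 85 were counted before or after the exclusion.

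The cost is wording in the eligibility, design and statistical sections. Enrolled no-opioid patients are already surveyed, and Section 6 already plans to draw prescriptions and return visits from the records. The separate study of recovery without opioids can still use these patients. The one small downside is a more skewed dose distribution because of the zeros.

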7 DATA COLLECTION AND MANAGEMENT PROCEDURES

- As noted above, the baseline survey will be administered via an online Qualtrics survey for patients recruited over the phone, and via Qualtrics on a tablet in-person for patients at Mott or University Hospital. Daily surveys on post-operative days 1-13 will be administered via an online Qualtrics survey, as will the final post-operative day 14 survey (with the exception of patients who cannot receive e-mail links, who will be administered the final survey over the phone, or patients who prefer to complete the survey over the phone).
- Data entry
 - Survey data obtained through Qualtrics will automatically be uploaded into a secure database.
 - All data extracted from DataDirect and MiChart will be manually entered into this secure database.
- Data management and security
 - Only study team members trained in human subjects protection will have access to study data
 - Only coded patient identifiers will be associated with study data. Only the PI will have the crosswalk between these identifiers and identifiable information such as patient name.
 - Electronic data files will be password-protected and stored on a secure server with restricted access.
 - Data will be destroyed within 90 days of completion of the study.

8 DATA ANALYSIS

- The primary analysis will examine changes in opioid prescribing and health care utilization.
- The secondary analysis will additionally examine changes in patient-reported outcomes..

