2 OBJECTIVES

- To evaluate changes in opioid prescribing, consumption, patient-reported outcomes, and health care utilization after implementation of a behavioral intervention using evidence-based default dosing settings for opioid prescriptions to adolescents and young adults undergoing tonsillectomy

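### No outcome in the primary analysis is named as decisive, and there is no significance level or multiplicity rule: the false-positive risk is about 10% for the two outcomes expected to change and about 23% for the five that can vary

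*Combined protocol and SAP*

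**What the plan says.** Section 8 defines the primary analysis by two domains: "The primary analysis will examine changes in opioid prescribing and health care utilization". Section 10, under "Outcomes in primary analysis", lists six outcomes:

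1. "Number of doses in the discharge opioid prescription"
2. whether that number equals the new default
3. "Proportion of patients prescribed opioids at discharge"
4. at least one refill, among those prescribed
5. an office visit for pain
6. an emergency visit or hospitalization for pain

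One model form serves all outcomes: "We will fit linear or logistic regression models assessing outcomes as a function of an indicator of post-intervention status", together with a group indicator and the interaction of the two.

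The hypotheses in Section 10 are directional. Doses and consumption should fall in the treatment group, the match to the new default should rise, and balancing measures should not change; pain control and depression are the examples given. Section 1 lists refill requests and return visits for uncontrolled pain among the possible unintended consequences.

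Section 10 also says "Subgroup analysis will occur by age group (ages 12-17 years vs 18 and older), gender, payer type (private/public), and baseline co-morbidities", with depression and anxiety as examples of co-morbidities. It does not say which outcomes the subgroup analyses cover.

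Section 4 excludes from the primary analysis "Patients who are not prescribed opioids post-operatively". Section 6 confirms that these patients enter neither the primary nor the secondary analysis.

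The objective in Section 2 reads "To evaluate changes in opioid prescribing, consumption, patient-reported outcomes, and health care utilization after implementation of a behavioral intervention" and ranks none of its four domains. No section gives a significance level, sidedness, testing order, success rule or multiplicity adjustment.

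**The concern.** A plan that calls several outcomes primary should say how they combine into a conclusion. This one does not. If the number of doses did not change but more prescriptions matched the default, nothing in the plan says whether the intervention succeeded. Nor does it say what to conclude if doses fell and refills rose. The number of doses and the match to the default are both expected to move, so either could be presented as the main result once the data are in. The error rate of the study's main claim is then not held at the level of a single test.

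The two are also not equally informative. Section 6 says the new orderset fills in the doses field with the default, so the match to the default is close to a check that the intervention was delivered.

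Separately, one listed outcome appears to have no variation in the population that the plan defines for it.

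**Working it through.** **The plan's own figures.** Section 10 gives only expected patient numbers.
- Primary analysis: 113 + 85 = 198, as stated.
- Secondary analysis: 0.65 × 113 = 73.45 (stated 74), 0.65 × 85 = 55.25 (stated 55), 0.65 × 198 = 128.7 (stated 129). These agree to within rounding.

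No power or effect size is attached to any outcome, so the sample-size text does not identify a deciding outcome either.

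**Inputs for the error rate.**
- Outcomes listed as primary: 6 (Section 10).
- Outcomes that can vary: 5. With patients not prescribed opioids removed (Sections 4 and 6), the share discharged with a prescription is essentially 100% in both groups and both periods, so its interaction term cannot produce a false positive.
- Primary-list outcomes hypothesized to change: 2, the number of doses and the match to the default (Section 10). Consumption is also expected to fall but is on the secondary list.
- Significance level: not stated. Assumed two-sided 0.05 per test; range shown below.
- Dependence between tests: not stated. Independence first, then a common correlation, then any dependence.

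**Formulas**, with k tests at level α and no true effect on any of them:
- independence: 1 − (1 − α)^k
- ceiling under any dependence: k × α

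**Results at α = 0.05.**
- k = 2: 1 − 0.95² = 1 − 0.9025 = 9.75%, about 10%; ceiling 2 × 0.05 = 10%.
- k = 5: 1 − 0.95⁵ = 1 − 0.7738 = 22.6%, about 23%; ceiling 5 × 0.05 = 25%.

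**With correlated test statistics** (simulation, 1,000,000 draws, equal correlation between all tests):

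| Correlation | k = 2 | k = 5 |
|---|---|---|
| 0.3 | 9.5% | 20.9% |
| 0.5 | 9.0% | 18.4% |
| 0.8 | 7.8% | 12.7% |

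Some positive dependence is plausible, because the number of doses and the match to the default are read from the same prescription.

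**With other significance levels, independence:**

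| α per test | k = 2 | k = 5 |
|---|---|---|
| 0.01 | 2.0% | 4.9% |
| 0.025 | 4.9% | 11.9% |
| 0.10 | 19.0% | 41.0% |

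**After the fix.** One deciding outcome tested once at 0.05 gives 5%.

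**The case against.** The best defence is that the plan is less open than its list suggests. Its hypotheses are fixed in advance with directions, and doses come first. Section 1 already treats refills and return visits as possible harms, so presenting a fall in visits as benefit would go against the plan's own framing. Section 4 also separates the two analyses by subject, prescribing against survey outcomes, so the word primary may describe a data source and population more than a confirmatory rank.

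Much of this stands. It is why the figure relevant to a claim of success is about 10%. It does not remove the problem: two primary-list outcomes are still expected to change, neither is ranked above the other, and coming first in a list is not a decision rule. The examples of balancing measures in Section 10 do not include refills or visits, which are listed alongside the benefit measures.

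Three stronger readings are tempting, and the documents do not support them:

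- A reader might take all six outcomes and quote 1 − 0.95⁶ = 26.5%. As the plan is written, one of the six cannot vary. The figure would apply only if that outcome were analysed in a population that includes patients not prescribed opioids. Independence is not the worst case either: the ceiling for six would be 30%.
- A reader might pool the six with the 18 further survey outcomes and quote 1 − 0.95²⁴ = 70.8%. Section 10 assigns those 18 to the secondary analysis, so this says nothing about the main claim.
- A reader might count ten subgroup levels on 24 outcomes and expect 240 × 0.05 = 12 false positives. Section 10 does not say that every level is tested on every outcome, and its co-morbidity factors are only examples.

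A Bonferroni rule would also control the error: 0.05/5 = 0.01 per test gives 4.9% under independence and at most 5% under any dependence. But it would test the number of doses at a stricter level and would leave benefit and harm measures in one family.

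**Conclusion.** The point holds in a limited form. The plan lists six primary outcomes and gives no deciding outcome, significance level or multiplicity rule. The chance of at least one false positive is about 10% across the two outcomes that could support a claim of success, roughly double the rate of a single test, and about 23% across the five that can vary. Both figures assume a two-sided 0.05 per test, which the documents do not state, independent tests, and no true effect on any outcome counted. Positive correlation lowers them; they cannot exceed 10% and 25% at that level.

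Separately, Sections 4 and 10 conflict over the share of patients discharged with an opioid prescription. The refill outcome limits its own denominator to patients prescribed opioids, which may mean that a wider population was intended for other items on the list, but the text does not say so.

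**What to change.** Add a short paragraph to Section 10 that:

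- names "Number of doses in the discharge opioid prescription" as the sole outcome that decides success, with its group-by-period interaction tested once at two-sided 0.05;
- calls the match to the new default a process measure;
- reports refills, office visits, and emergency visits or hospitalizations for pain as balancing measures with 95% intervals, not as evidence of benefit;
- limits subgroup testing to the group × period × subgroup term for the number of doses, and labels all other subgroup results exploratory;
- reconciles Sections 4 and 10 on the share discharged with a prescription, for example by analysing that outcome in a population that includes patients not prescribed opioids.

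This needs no extra patients or data and loses no power for the number of doses. The cost is that the other outcomes can no longer be claimed as primary results.
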